3.1.2 Exclusion Criteria

① Received any local treatment during the targeted - immunotherapy combination treatment (including during treatment and within 4 weeks after treatment interruption), including:

Transcatheter arterial chemoembolization (TACE), transcatheter arterial embolization (TAE), drug - eluting bead transcatheter arterial chemoembolization (DEB - TACE) and other vascular interventional therapies;

Radiofrequency ablation, microwave ablation, cryoablation, laser ablation and other ablation therapies;

Stereotactic body radiation therapy (SBRT), three - dimensional conformal radiation therapy, intensity - modulated radiation therapy and other local radiation therapies;

Intratumoral injection therapy, high - intensity focused ultrasound (HIFU) and other local physical/chemical therapies.

② Local treatment was initiated before the start of targeted - immunotherapy combination treatment, and the local treatment continued into the targeted - immunotherapy treatment period (that is, there was an overlap between local treatment and targeted - immunotherapy treatment or the interval was < 4 weeks).

③ Complicated with other active malignant tumors (except for those with cured basal cell carcinoma of the skin, carcinoma in situ of the cervix, and papillary thyroid carcinoma with no recurrence for more than 5 years after surgery).

④ Severe impairment of important organ functions:

Liver function: Child - Pugh class C, or total bilirubin > 3 × ULN;

Renal function: Serum creatinine > 1.5 × ULN and estimated glomerular filtration rate (eGFR) < 50 ml/min;

Cardiac function: New York Heart Association (NYHA) cardiac function class III - IV, or left ventricular ejection fraction (LVEF) < 50%.

⑤ Have uncontrolled active infections, including:

Hepatitis B virus DNA > 2000 IU/ml (without receiving antiviral treatment);

Hepatitis C virus RNA positive and without receiving antiviral treatment;

Active tuberculosis infection, septicemia, etc.

⑥ Have a history of autoimmune diseases and currently still need to use systemic glucocorticoids (prednisone > 10 mg/day) or other immunosuppressive therapies.

⑦ Pregnant or lactating women, or patients planning to become pregnant during the study.

⑧ Have a definite history of allergy to the targeted drugs or immune checkpoint inhibitors involved in the study.

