3.1.3 Withdrawal Criteria

- ① The subject voluntarily requests to withdraw from the study and signs a written withdrawal statement.
- ② Severe adverse events occur during the study (such as grade 3 or above immune - related adverse reactions, severe infections, etc.), and after the researcher's evaluation, it is considered that continued participation in the study may endanger the subject's safety.
- ③ The subject does not comply with the research protocol, including but not limited to: failure to follow up at the specified time, refusal to complete necessary examinations, unauthorized acceptance of other antineoplastic treatments, etc.
- ④ It is found during the study that the subject does not meet the inclusion criteria of this study (such as the previous treatment history does not meet the requirements found in the baseline data verification).
- ⑤ The subject is unable to continue participating in the study due to disease progression, death, and other reasons.
- ⑥ The study is terminated in advance (such as protocol revision, ethical committee requiring termination, etc.).

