3.2.2 Immunotherapy Response Evaluation System

3.2.2.1 Primary Observation Indicators

(1) Time to Progression (TTP)

Definition: The time from the start of targeted - immunotherapy combination treatment to

the first time meeting the mRECIST progression criteria.

Evaluation Criteria:

Target lesions: The sum of the diameters of arterial - phase enhancement increases by $\geq 20\%$ compared to the baseline and the absolute value $\geq 5\text{mm}$;

Non - target lesions: New lesions appear or existing non - target lesions have definite progression;

Distant metastasis: New occurrences of lung, bone, or lymph node metastases.

(2) Objective Response Rate (ORR)

Definition: The proportion of patients achieving complete response (CR, disappearance of arterial - phase enhancement in all target lesions) and partial response (PR, the sum of the diameters of target lesions is reduced by $\geq 30\%$).

Evaluation Time: For each line of targeted - immunotherapy combination treatment regimen received by the patient, the determination is made simultaneously at Week 8, Week 16, Week 24 of the regimen treatment, and at disease progression (or regimen termination). If the patient changes the targeted - immunotherapy treatment regimen due to poor efficacy, the treatment cycle of the new regimen needs to be recorded separately (Weeks 8, 16, 24 are recalculated from the start time of the new regimen), and the CR/PR status is evaluated at the corresponding time points. In the final ORR calculation, the CR/PR status achieved by the patient in a certain regimen only corresponds to the treatment cycle and evaluation time of that regimen, that is, it is clearly associated with the efficacy data of the specific targeted - immunotherapy combination regimen (including the first regimen or the subsequent new regimens).

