3.2.2.2 Secondary Observation Indicators

(1) Core Indicators of Immunotherapy Response

① Progression - Free Survival (PFS)

Definition: The time from the start of targeted - immunotherapy combination treatment to the first disease progression (determined according to mRECIST) or death from any cause, whichever occurs first.

Evaluation Method: Combine imaging examinations (once every 8 weeks) and survival status follow - up, and use the Kaplan - Meier method to perform Log - rank test to compare the differences between groups.

② Overall Survival (OS)

Definition: The time from the start of targeted - immunotherapy combination treatment to the patient's death from any cause; for lost - to - follow - up patients, the last follow - up date is used as the censored data.

Evaluation Method: Record the survival status through regular telephone/outpatient follow - up, draw survival curves, and analyze the differences between groups.

Dynamic changes of tumor markers.

(2) Dynamic Monitoring Related to Tumors

Dynamic changes of tumor markers

Monitoring Indicators: Alpha - fetoprotein (AFP), protein induced by vitamin K absence or antagonist - II (PIVKA - II), detected once at baseline and every 4 weeks.

Judgment Criteria: An increase of $\geq 20\%$ compared to the baseline and lasting for more than 4 weeks, combined with imaging results to assist in predicting the progression

risk (such as the early warning value of marker increase before imaging progression).

(3) Evaluation of Treatment - Related Status

① Correlation with Liver Function Status

Evaluation Nodes: Collect liver function data (Child - Pugh class, total bilirubin, albumin, INR) simultaneously when disease progresses.

Analysis Logic: Compare with baseline liver function, exclude interfering factors such as drug - induced liver injury, and evaluate the direct impact of tumor progression on liver function injury.

② Survival Analysis after Progression

Record Content: Treatment adjustment plans after disease progression (changing targeted drugs, adding local treatments, etc.).

Analysis Indicators: Post - progression survival (PPS, the time from disease progression to death or the end of the study), and analyze the impact on survival by combining differences in treatment plans.

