3.2.3.2 Survival Analysis

Use the Kaplan - Meier method to draw survival curves of time to progression (TTP) and post - progression survival (PPS), and compare the survival differences between the new typing cohort and other typing cohorts through Log - rank test; use the Cox proportional hazards regression model to analyze the impact of 29 - gene set typing and clinical factors (such as Child - Pugh class, changes in tumor markers) on the progression risk.

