3.2.4 Protection Measures for Vulnerable Groups

The vulnerable groups that may be involved in this study include the mentally ill/cognitively impaired/critically ill patients/elderly/illiterate, etc. This study will take the following measures to protect their interests: 1) Ensure that the subjects are fully informed. If the subject is unable to read and sign the informed consent form due to

incapacity, their guardian shall act as the agent for the informed process and sign the informed consent form. If the subject is unable to read the informed consent form (such as illiterate subjects), a witness shall witness the informed process and sign the informed consent form. 2) If it is a critically ill patient, the researcher will closely monitor the vital signs of such subjects, and report in a timely manner once there is a situation.

IV. Sample Size Calculation

This study plans to include subjects from 10 top - three hospitals nationwide. Calculate the new typing score of HCC for each sample through the 29 - gene signature. It is estimated that there will be 100 cases in the new typing cohort and 250 cases in other typing cohorts.

Therefore, the final planned total sample size of this study is 350 cases.

V. Data Management and Confidentiality

All records related to the subject's identity will be kept confidential, and these materials will not be disclosed outside the scope permitted by relevant laws and/or regulations.

VI. Informed Consent

For the prospective observational study part involved in this study, before the subjects are included in this study, the researcher responsible for the informed consent discussion should introduce the purpose, nature, procedure, and possible benefits and risks of this study to them in written form completely and comprehensively. The subjects should be informed that they have the right to withdraw from the study at any time. Before inclusion, each subject should be fully informed and have sufficient time to consider whether to participate. Only after the subject voluntarily participates and signs the informed consent form can they be included in this study.

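### Exclusion ① does not stop at progression, so it removes an unknown and selected share of the patients whose post-progression local treatment section 3.2.2.2 plans to analyse

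*Protocol*

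**What the plan says.** Protocol 3.1.2, item ①, excludes a patient who "Received any local treatment during the targeted - immunotherapy combination treatment (including during treatment and within 4 weeks after treatment interruption". The listed treatments cover vascular intervention, ablation, local radiotherapy and intratumoral or physical methods. Progression is not mentioned as an end of the window.

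Protocol 3.2.2.1 (2) expects further lines of combination treatment. It begins a rule with "If the patient changes the targeted - immunotherapy treatment regimen due to poor efficacy" and then restarts the Week 8, 16 and 24 response assessments for the new regimen.

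Protocol 3.2.2.2 (3) ② sets out what is recorded for survival after progression: "Treatment adjustment plans after disease progression (changing targeted drugs, adding local treatments, etc". The analysis there is of post-progression survival (PPS), and the plan is to "analyze the impact on survival by combining differences in treatment plans".

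Protocol 3.2.3.2 names one formal PPS test, by subtype: "compare the survival differences between the new typing cohort and other typing cohorts through Log - rank test".

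Two withdrawal items in 3.1.3 bear on the same patients. Item ③ includes "unauthorized acceptance of other antineoplastic treatments". Item ⑤ reads "The subject is unable to continue participating in the study due to disease progression, death, and other reasons".

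**The concern.** A patient who progresses and then has local treatment added to a continuing or switched combination, or within 4 weeks of stopping it, meets exclusion ①. The same patient belongs to a category that 3.2.2.2 (3) ② names for analysis. Nothing in the protocol limits the exclusion to the time before progression or defines a separate PPS population.

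Two things are at stake. First, the local-treatment category of the PPS analysis loses members according to when they were treated, so those who remain do not represent patients given local treatment after progression. Second, a patient whose first progression has been observed has already supplied the event for TTP (a primary indicator) and for PFS. Removing that patient because of a later treatment selects the cohort on an event after the endpoint, and every patient removed in this way is a progressor.

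**Working it through.** **Step 1: set the rules side by side.** Possible courses after first progression:

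| Course after first progression | Exclusion ① (3.1.2) | PPS by treatment plan (3.2.2.2) |
|---|---|---|
| Local treatment while the same combination continues | removed | wanted |
| Local treatment during a new combination line (3.2.2.1) | removed | wanted |
| Local treatment within 4 weeks of stopping | removed | wanted |
| First local treatment more than 4 weeks after stopping, and not during a later line | kept | wanted |
| No local treatment | kept | comparator |

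Three of the four local-treatment courses are removed and one is kept. The table does not say how many patients follow each course, and neither does the protocol.

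**Step 2: who is left.** PPS runs from progression. A patient who stopped the combination at or after progression and is kept in the local-treatment group must have lived more than 4 weeks past progression before that treatment began. The comparator has no such requirement. An unadjusted comparison from progression therefore favours the local-treatment group. If the combination had stopped before progression, this guaranteed time is shorter.

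**Step 3: the plan's own figure.** Section IV says "It is estimated that there will be 100 cases in the new typing cohort and 250 cases in other typing cohorts"; 100 + 250 = 350, as stated. No figure is given for PPS or for local treatment, so there is nothing further to reproduce.

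**Step 4: an illustration of size.** Inputs:
- N = 350 (Section IV).
- Share progressing p = 0.60. This borrows the background figure for drug resistance in Section I; it is a proxy, not a progression rate for this cohort.
- Share of progressors given local treatment, l = 0.10, 0.20 or 0.40 (assumed).
- Share of those first treated after the 4-week window, s = 0 to 0.50 (assumed).

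Progressors: 350 × 0.60 = 210. Local-treatment patients without the exclusion: 210 × l. Kept with it: 210 × l × s.

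| l | without ① | s = 0 | 0.05 | 0.10 | 0.25 | 0.50 |
|---|---|---|---|---|---|---|
| 0.10 | 21 | 0 | 1.1 | 2.1 | 5.3 | 10.5 |
| 0.20 | 42 | 0 | 2.1 | 4.2 | 10.5 | 21 |
| 0.40 | 84 | 0 | 4.2 | 8.4 | 21 | 42 |

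With p = 0.80 (280 progressors) the column without ① is 28, 56 and 112, and the largest number kept is 56.

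**Step 5: what that does to precision.** Schoenfeld's formula, two-sided 0.05: power = Φ(|ln HR| × √(D × q × (1 − q)) − 1.96), where D is deaths and q is the local-treatment share. Assume HR 0.6, 70% deaths and l = 0.20.
- Without ①: D = 0.70 × 210 = 147 and q = 0.20. √(147 × 0.16) = 4.85; 4.85 × 0.511 − 1.96 = 0.52; power 0.70.
- With ① and s = 0.25: 210 − 42 + 10.5 = 178.5 progressors, D = 124.95, q = 10.5/178.5 = 0.059. √(124.95 × 0.0554) = 2.63; 2.63 × 0.511 − 1.96 = −0.62; power 0.27.
- At s = 0.05, 0.10 and 0.50 the same steps give 0.09, 0.14 and 0.45.

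**Step 6: the effect on observed progressions.** In the same case (l = 0.20, s = 0.25), 42 − 10.5 = 31.5 progressors are removed and no non-progressors. The progressing share falls from 60% to 178.5/318.5 = 56.0%. Whether this distorts the subtype comparison depends on whether local treatment is used differently by subtype, which the documents do not say.

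Steps 4 to 6 assume the exclusion is applied to everyone and that removed patients are not replaced.

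**The case against.** A reader might infer that the two sections cannot both be followed, or that the local-treatment group will be almost empty. The documents support neither. Local treatment more than 4 weeks after stopping the combination satisfies both rules. The window runs from interruption of treatment, not from progression, so a patient who stopped early and progressed later may have local treatment straight away and still be kept. The timing of local treatment is not given, and the assumed shares leave anything from 0 to 42 patients.

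The reach of the exclusion is also uncertain. Section VI describes a prospective part, where post-progression treatment happens after entry and cannot be screened for at enrolment. Section 3.1.3 does not make a later breach of an exclusion criterion a ground for withdrawal: item ④ refers to inclusion criteria, and item ③ only to unauthorised treatment. Prospective patients may therefore stay. In the retrospective part, excluded patients would be screened out beforehand and could be replaced, so the counts above are not necessarily losses from the 350. The split between the two parts is not stated.

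The affected analysis is secondary, and local treatment is one example in an open list. The PPS test by subtype in 3.2.3.2 can still be run, though on a selected cohort.

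Finally, simply ending the exclusion at first progression would do harm. ORR in 3.2.2.1 is tied to each regimen, including later ones, and a response after local treatment during a later line would be credited to that regimen. This is a plausible reason for the window to run on, and any repair has to deal with it.

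All of this stands. It limits the size of the problem and shapes the repair, but it does not remove the mismatch: no section says which rule governs these patients.

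**Conclusion.** The point holds as a mismatch between an eligibility rule and a stated secondary analysis. Exclusion ① has no end at progression and later combination lines extend it, yet the effect of local treatment added after progression is to be analysed. Where the exclusion is applied, notably in the retrospective part, the remaining local-treatment group is selected on late treatment and on survival to it. The comparison is then biased and of unknown size, and some observed first progressions are discarded because of a later event.

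The conclusion about selection rests on the text alone. The size does not: 21 to 84 patients before the exclusion, 0 to 42 after it, and power falling from 0.70 to between 0.09 and 0.45 at a 20% local-treatment share all depend on assumed shares, an assumed HR of 0.6 and 70% deaths. The point should be corrected before analysis, but it does not invalidate the subtype comparison.

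**What to change.** Reconcile 3.1.2 ①, 3.1.3, 3.2.2.1 (2) and 3.2.2.2 (3) ②. How far the exclusion is meant to reach is for the sponsor and investigators to decide; either of two versions would be consistent.

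- **If it is meant to end at progression:** state that for TTP, PFS, OS and PPS exclusion ① applies only up to first mRECIST progression. Keep patients given local treatment later, with its date. Leave any later-line regimen with concurrent local treatment out of that line's ORR.
- **If it is meant to run past progression:** remove local treatment from the post-progression treatment plans to be analysed, and state that its effect on survival cannot be studied in this cohort.

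In both versions, say how the rule applies to prospective patients who receive local treatment after entry, and whether the withdrawal items in 3.1.3 cover them.

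The cost is a short amendment and, in the first version, one extra analysis-population rule for later-line ORR. No new data are needed, because post-progression treatment is already to be recorded.

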3.1.3 Withdrawal Criteria

- ① The subject voluntarily requests to withdraw from the study and signs a written withdrawal statement.
- ② Severe adverse events occur during the study (such as grade 3 or above immune - related adverse reactions, severe infections, etc.), and after the researcher's evaluation, it is considered that continued participation in the study may endanger the subject's safety.
- ③ The subject does not comply with the research protocol, including but not limited to: failure to follow up at the specified time, refusal to complete necessary examinations, unauthorized acceptance of other antineoplastic treatments, etc.
- ④ It is found during the study that the subject does not meet the inclusion criteria of this study (such as the previous treatment history does not meet the requirements found in the baseline data verification).
- ⑤ The subject is unable to continue participating in the study due to disease progression, death, and other reasons.
- ⑥ The study is terminated in advance (such as protocol revision, ethical committee requiring termination, etc.).

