For the retrospective study part involved in this study, if it only involves the use of previously saved clinical data and biological specimens, does not interfere with the clinical diagnosis and treatment process, and will not have an adverse impact on the health of the subjects. During statistical analysis, the identity of the subjects is represented by codes, and there is no disclosure of the subjects' privacy and personal information. This part of the study does not involve commercial interests and can apply for exemption from informed consent.

VII. Adverse Events and Related Handling Measures

For the prospective observational study part involved in this study, only clinical data of the subjects are collected, no additional biological samples are collected, and the clinical diagnosis and treatment process is not interfered with, which will not have an adverse impact on the health of the subjects.

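### Section 3.1.3 withdraws patients from a purely observational study for toxicity, missed visits, other anticancer treatment or progression, and nothing in the protocol keeps them in follow-up

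*Protocol*

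**What the plan says.** Protocol section 3.1.3 lists six reasons for withdrawal. Three matter here.

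- Item 2: a severe adverse event, for example an immune-related reaction of grade 3 or above, provided that on the researcher's evaluation "it is considered that continued participation in the study may endanger the subject's safety".
- Item 3: non-compliance, which includes "failure to follow up at the specified time, refusal to complete necessary examinations" and "unauthorized acceptance of other antineoplastic treatments".
- Item 5: "The subject is unable to continue participating in the study due to disease progression, death, and other reasons".

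The design is observational. Section VII says of the prospective part that "no additional biological samples are collected, and the clinical diagnosis and treatment process is not interfered with". Section VI describes the retrospective part as using stored data and specimens without interfering with care. Section 3.2.1.2 takes treatment, imaging and survival status from the electronic medical record.

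The outcome definitions follow patients past the events in 3.1.3. Section 3.2.2.1 restarts the Week 8, 16 and 24 response assessments "If the patient changes the targeted - immunotherapy treatment regimen due to poor efficacy". Section 3.2.2.2 follows overall survival (OS) to death from any cause, by telephone or outpatient contact. For post-progression survival (PPS) it records "Treatment adjustment plans after disease progression (changing targeted drugs, adding local treatments, etc".). Its only explicit censoring rule concerns OS in patients lost to follow-up.

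**The concern.** Withdrawal rules of this kind suit a trial that gives a study drug, where leaving treatment and leaving the study can be confused. Here there is no study treatment to stop, so the only thing a patient can leave is data collection.

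The triggers are not neutral. Severe toxicity, missed visits, a switch to other anticancer treatment and progression all arise after treatment starts and may reflect how it is working. The Kaplan-Meier, log-rank and Cox analyses in section 3.2.3.2 assume that censoring is unrelated to prognosis within groups. A response rate computed only on those who remain describes a selected group. The study expects response to differ by subtype (section II), so the losses could differ by subtype as well. Time to progression (TTP) and objective response rate (ORR) are the primary indicators, and progression-free survival (PFS) and OS are the core secondary ones.

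**Working it through.** **The plan's own figure.** Section IV gives 100 + 250 = 350 patients. It gives no effect size, power, event count or dropout rate. The point does not rest on 350, and no stated figure is contradicted.

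**Rules against outcomes**

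| 3.1.3 trigger | Data still needed | Consequence if collection stops |
|---|---|---|
| Item 5, progression | OS to death; PPS, which starts at progression | OS is censored at progression and PPS has no follow-up. TTP and PFS are unaffected, because their event has occurred. |
| Item 3, other anticancer treatment | OS; PPS if it follows progression; TTP, PFS and ORR if it precedes progression | Depends on what counts as unauthorized, which is not defined. |
| Item 3, missed visits or refused examinations | Survival status, obtainable by telephone or from records | OS is lost although obtainable. Imaging never done cannot be recovered. |
| Item 2, severe toxicity with the safety judgement | TTP, PFS, OS and any later response assessment | Follow-up ends on a case-by-case judgement. |

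Item 5 is the most direct conflict: the event that starts the PPS clock is also listed as a reason to leave the study.

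**Illustration for ORR.** All rates are assumed. Let p be the true ORR, w the share withdrawn and dropped from the denominator, and r the response rate among the withdrawn.

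Observed ORR = (p − w·r) / (1 − w)

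Take p = 0.30 in both groups, w = 0.10 in the new subtype (10 of 100 leave) and w = 0.20 in the others (50 of 250 leave).

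| r | New subtype, 90 left | Others, 200 left | Spurious gap |
|---|---|---|---|
| 0 | 0.300/0.90 = 33.3% | 0.300/0.80 = 37.5% | 4.2 points |
| 0.15 | 0.285/0.90 = 31.7% | 0.270/0.80 = 33.8% | 2.1 points |
| 0.30 | 0.270/0.90 = 30.0% | 0.240/0.80 = 30.0% | 0 |

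Swapping the two withdrawal shares reverses the sign. For scale, the standard error of the difference at 90 and 200 patients is √[0.30 × 0.70 × (1/90 + 1/200)] = 0.058, about 6 points.

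**Illustration for TTP.** Assume exponential TTP, a true hazard ratio (HR) of 1.0, and a share q censored at 80% of their own time to progression. That is strongly informative by construction. The observed rate is the true rate times (1 − q)/(1 − 0.2q):

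- q = 0.10: 0.90/0.98 = 0.918
- q = 0.20: 0.80/0.96 = 0.833
- q = 0.30: 0.70/0.94 = 0.745

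Apparent HR, new subtype against others:

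- 10% and 20% withdrawn: 0.918/0.833 = 1.10
- 20% and 10% withdrawn: 0.833/0.918 = 0.91
- 10% and 30% withdrawn: 0.918/0.745 = 1.23
- 30% and 10% withdrawn: 0.745/0.918 = 0.81

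With equal shares the HR stays at 1.0, but median TTP is overstated. A simulation with a true median of 8 months gave about 8.8, 9.8 and 11.1 months at 10%, 20% and 30% withdrawn.

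**The case against.** Several objections carry weight.

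- **Item 2 is conditional.** The researcher must also judge participation unsafe. Since observation itself poses no such danger, the rule might rarely be used. That limits its reach. It does not justify keeping a rule that could end data collection by individual judgement, with no blinding to subtype described.
- **The protocol does not literally say that observation stops.** This stands as a matter of wording. But the rules concern participation, the study consists of nothing but data collection, and no section keeps withdrawn patients in follow-up.
- **A reader might infer a flat contradiction between item 3 and sections 3.2.2.1 and 3.2.2.2.** The documents do not support that. Section 3.2.2.1 covers changes of the targeted-immunotherapy regimen, and the treatment recorded in 3.2.2.2 follows progression. Item 3 can be read as the on-study counterpart of exclusions 1 and 9 in section 3.1.2, which keep out local treatment and other antineoplastic drugs during combination therapy. The conflict is partial and turns on an undefined word.
- **Analysis handling may sit in a statistical analysis plan (SAP) not shown here.** This stands for censoring choices. It does not stand for data that were never collected.
- **Retrospective patients are largely untouched**, having already been treated. The rules bite mainly on the prospective part, whose share is not stated.
- **The 4.2-point gap is the top of the range shown.** Response is assessed from Week 8, so it may precede withdrawal, and nothing says that withdrawn patients leave the denominator.

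**Conclusion.** The point holds as a defect of the stated rules. Followed as written, items 2, 3 and 5 can take patients out of an observational study for reasons plausibly related to outcome, while the outcome definitions still need their data. Item 5 is the clearest case, for OS and PPS. Items 2 and 3 may affect TTP, PFS, OS and ORR.

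A reader might infer that the results will be biased in favour of the new subtype, or by a known amount. The protocol supports neither. With the assumed shares above, the spurious ORR gap runs from zero to 4.2 points and can point either way. The apparent HR runs from 0.81 to 1.23 under a deliberately strong assumption. All of this depends on withdrawal rates, timing and response among the withdrawn, none of which the protocol gives. The change should be made because it is cheap and because the loss cannot be repaired at analysis.

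**What to change.** 1. In section 3.1.3, limit study exit to withdrawal of consent (item 1), ineligibility found at verification (item 4), death, and termination of the study (item 6).
2. Record the remaining events in items 2, 3 and 5 as dated events: severe toxicity, missed visits or refused examinations, other anticancer treatment, and progression.
3. State that imaging and survival status continue to be collected from routine records after these events, that patients who started combination treatment stay in the ORR denominator, and that OS is followed to death.
4. Reconcile 3.1.3 with 3.1.2 (exclusions 1 and 9), 3.2.2.1, 3.2.2.2 and Section VII. In particular, say what unauthorized treatment means in a study that directs none, and how a patient who receives local or other anticancer treatment during combination therapy is classified.
5. Leave to the SAP whether TTP and PFS are censored at other anticancer treatment. Either choice is a trade-off, so show the alternative as a sensitivity analysis.

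This concerns data retention only and proposes no clinical rule; care decisions stay with the treating team. The cost is a change of wording and slightly more record retrieval. Imaging that a patient refuses will still be missing.
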